### **5.2. Volume of Blood Sampling**

Total blood volumes required during study participation will be provided in PIS/ICF provided to each patient. The Lab Manual will also describe the unit and total blood volumes and provide examples based on various durations on study. Efforts will be made to limit PK and PD blood-letting during the study where on-going data analysis during the study suggests redundancy in sampling. Any such reductions in requirements for PK and PD blood sampling will be described and updated in the Lab Manual.

### **5.3. Description of Study Interventions and Assessments**

Details of the procedures to be followed for specified study assessments are provided. Additional assessments may be carried out as clinically indicated.

#### **5.3.1. Medical history**

There will be a baseline assessment of medical history conducted at Screening to confirm eligibility and to record significant medical history and concurrent illnesses in the eCRF. Concurrent illnesses recorded at Screening, that worsen in severity or frequency from this baseline assessment during the study, should be recorded and reported as AEs (see [Section 7](#)).

All prior therapy for the treatment of AML must be recorded in eCRF including, but not limited to, start date, stop date and best response.

### **5.3.2. Pregnancy and FSH test**

Female patients of reproductive potential will have a pregnancy test carried out at Screening. This test must be carried out within 7 days prior to first SEL24/MEN1703 administration. Alternatively, pregnancy test may be performed at C1D1 and results should be available prior to receiving study treatment. Additionally, a pregnancy test is required on the first day of each study cycle and after relevant systemic exposure can be reasonably excluded (30 days from the last study drug administration). A urine test is acceptable; however, where a urine test is positive or equivocal, a blood test must be performed to confirm the result. Patients confirmed as pregnant will be excluded from participation in the clinical study.

Please refer to [Section 7.7.1](#) for further instructions on the management of a positive urine test during the study conduct.

Female patients who require documented confirmation of post-menopausal status will have their follicle-stimulating hormone (FSH) levels assessed at Screening. When post-menopausal status is not confirmed, patients will be required to undergo pregnancy testing per protocol to confirm suitability to proceed.

### **5.3.3. ECOG performance status**

ECOG PS will be assessed at the times given in the Schedule of Study Assessment (Table 5). Details of the ECOG PS categories are presented in [Appendix A](#). Patients must be confirmed as ECOG PS 0, 1 or 2 at Screening in order to be eligible for study participation.

### **5.3.4. Vital signs**

Vital sign parameters will be taken at the times given in the Schedule of Study Assessment (Table 5). The date and time of collection will be recorded in the source data and on the eCRF.

Vital sign parameters will consist of measurements of temperature, resting heart rate, seated blood pressure and respiratory rate.

### **5.3.5. Physical examinations**

A physical examination, including measurement of weight, will be taken at the times given in the Schedule of Study Assessment (Table 5). The patient's height will be measured at Screening. The patient's weight will also be assessed at Screening and at the start of every cycle. Height and body weight will be obtained while the patient is wearing light clothing (without shoes).

A full physical examination will include assessment of the following categories: head, eyes, ears, nose, throat, heart, lungs, abdomen, skin, musculoskeletal, extremities, neurological, lymph nodes, and 'other'. After the Screening assessment, the physical examination may be reduced to a symptom-directed assessment.

### 5.3.6. Clinical chemistry, hematology, coagulation, lipid profile and urinalysis

Blood and urine samples for determination of clinical chemistry, hematology, coagulation, lipid profile and urinalysis parameters will be taken at the times given in the Schedule of Study Assessment (Table 5). The date and time of collection will be recorded in the source data and on the CRF.

All testing will be performed at each site's local laboratory. Patients should be asked to follow local guidance for fasting prior to the lipid profile assessment. At time points where coagulation testing is performed, these parameters may be assessed from the hematology sample. Should a patient develop coagulation abnormalities at any point during the study, a comprehensive evaluation of coagulation abnormalities will be immediately performed which may include, but not be limited to repeat PT/INR, APTT, fibrinogen, D-dimer, plus a peripheral blood smear, thrombin time. These abnormalities have to be evaluated by the Investigator in conjunction with the patient's medical history, physical examination and concomitant medication review. Repeat testing may be performed as clinically indicated, which may include additional parameters or time-points. Additional tests will be performed as required to rule out other etiologies.

Copies of laboratory accreditation certificates and reference ranges will be obtained from each study site prior to the analysis of their first patient sample.

The laboratory variables to be measured are described in [Appendix E](#).

Results from the hematology test panel will contribute to each patient's disease assessment (see [Section 5.3.11](#)).

### 5.3.7. Peripheral blasts

Assessment of peripheral blasts will be part of the hematology panel at the time-points specific in the Schedule of Study Assessment (Table 5).

Results from these assessments will contribute to each patient's disease assessment (see [Section 5.3.11](#)).

### 5.3.8. Electrocardiograms

A resting 12-lead ECG will be performed at the times given in the Schedule of Study Assessment (Table 5).

All 12-lead ECGs should be recorded while the patient is in the supine position. ECGs will be recorded at 25 mm/sec. All efforts should be made to ensure that an identical ECG machine is used to collect traces for individual patients. The Investigator or designated physician will review the ECG results.

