**Table 2: Part 2 Study Objectives and Endpoint (Assessment)**

Objective	Endpoint (Assessments)
Primary:	

 
To further characterize the safety profile of single agent SEL24/MEN1703
 
	
 
The number and frequency of AE, safety laboratory, vital signs and ECG assessments
 

Secondary:	

 
To assess anti-leukemic activity of single agent SEL24/MEN1703
 
	
 
Assessment of bone marrow and peripheral blast % and other assessments of clinical benefit including ORR (CR, CRi, CRh and MLFS), PR rate, DoR, RFS, EFS, OS, transfusion conversion rate, transfusion maintenance rate, HSCT rate
 

 
To evaluate the PK profile of SEL24/MEN1703 and its metabolites, as appropriate
 
	
 
Assessment of PK variables, including <math>C_{max}</math>, AUC and <math>t_{1/2}</math>
 

Exploratory:	

 
To assess the PD activity of SEL24/MEN1703
 
To assess the genetic profile of AML cells
 
	
 
Flow cytometry assessment of relevant biomarkers (e.g. pS6)
 
Analysis of relevant mutations in peripheral blasts and bone marrow by using Next Generation Sequencing and/or qRT-PCR
 

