### 1.3. Non-Clinical Studies with SEL24/MEN1703

SEL24/MEN1703, a potent PIM and FLT3-ITD dual activity inhibitor, demonstrates significantly broader activity in AML cell lines and primary AML blasts, irrespective of FLT3 status, than selective FLT3-ITD or PIM inhibitors.

*In vitro* studies and *in vivo* nonclinical pharmacology studies in mouse leukemia human xenograft models have been conducted to evaluate the anticancer potential of SEL24/MEN1703. Evaluation of SEL24/MEN1703 by enzymatic assay and biomarker studies shows that it exhibits potent activity on PIM kinase isoforms comparable with AZD1208, and slightly lower activity than quizartinib for the FLT3 mutant.

SEL24/MEN1703 demonstrates strong cytotoxic effects in AML cell lines, independently of FLT3 status, in contrast to quizartinib and AZD1208, which show more narrow therapeutic potential.

The unique mechanism of inhibiting both PIM and FLT3 kinases translates into potent effects in *in vivo* models. SEL24/MEN1703 shows anticancer effects in subcutaneous xenografts AML models and is superior to quizartinib and AZD1208, depending on the genetic background of mutations. Nonclinical pharmacology study results suggest that SEL24/MEN1703 may offer a comprehensive approach to targeting the PIM/FLT3 axis in AML patients and that the activity can be further enhanced by combination with standard chemotherapy.

*In vitro* and *in vivo* safety pharmacology studies have been conducted. *In vitro* studies included nuclear receptor binding studies, hERG inhibition and hERG tail currents recorded from transfected HEK293 cells. An *in vivo* GLP study has been conducted in male Beagle dogs to evaluate the effects on cardiovascular and neurobehavioral functions.

SEL24/MEN1703 was tested on a panel of G-protein-coupled receptors (GPCRs) and other receptors. The compound was tested at the high concentration of 10  $\mu$ M. Three receptors were identified as inhibited more than 85% (NK1, 5HT2B, and sigma). Both receptors were tested for agonistic and antagonistic activity of SEL24/MEN1703. No agonistic activity was detected.

Results of evaluation of hERG currents indicated that for SEL24/MEN1703, the hERG IC50 was 3.561  $\mu$ M. For the positive control, E-4031, the mean hERG inhibition was 88.5%. In addition, SEL24/MEN1703 inhibited hERG tail current in HEK293 cells stably transfected with hERG cDNA with an estimated IC50 value of 2.5  $\mu$ M.

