16. Received an agent known to be a sensitive CYP2D6 substrate or a CYP2D6 substrate with a narrow therapeutic range, a strong or moderate CYP2D6 inhibitor, or a BCRP inhibitor within 7 days or a period corresponding to 4-5 half-lives of the agent, prior to the first dose of study drug.
17. Cardiac dysfunction defined as myocardial infarction within 6 months of study entry, New York Heart Association (NYHA) Class III or IV heart failure, uncontrolled dysrhythmias or poorly controlled angina.
18. Are receiving any active treatment for thrombosis.
19. History of serious ventricular arrhythmia (e.g. VT or VF,  $\geq 3$  beats in a row), or QT interval corrected for heart rate (QTc)  $\geq 480$  ms.  
*Note: QTc values up to 500 ms will be acceptable where patient's medical history e.g. bundle branch block, is known to cause mild QTc prolongation and the condition is well controlled.*
20. Any disease, syndrome or condition which may affect significantly drug intake via oral route.
21. Any other prior or current medical condition, intercurrent illness, surgical history, physical or 12-lead electrocardiogram (ECG) findings, laboratory abnormalities, or extenuating circumstance (e.g. alcohol or drug addiction) that, in the investigator's opinion, could jeopardize patient safety or interfere with the objectives of the study.

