11.5. Safety analysis

Safety and tolerability assessments will be evaluated on the safety population by means of descriptive statistics. Summary statistics (counts / (%) | number of events) will report the incidence of AEs using combinations of these variables for the descriptive statistics stratification: CTCAE toxicity grade, relationship with study drug, seriousness, System Organ Class or Body System, Preferred Term.

AEs summary tables will be created by Cohort (dose level) and Overall.

Counts and percentages will be produced for the results of the ECG, laboratory values (clinical chemistry, haematology, coagulation, bone marrow and urinalysis), vital signs, physical examination, classified as Normal/Abnormal NCS/Abnormal CS by Cohort (dose level) and Overall, stratified by Visit and timepoint – if applicable.

For ECG and hematology, clinical chemistry, coagulation and bone marrow laboratory data, the change from baseline will be summarized for each post baseline visit with descriptive statistics by cohort. For hematology and clinical chemistry laboratory parameters shift tables will be presented with the counts of individual shifts from each of the reference range categories from baseline to the worst post-baseline value by laboratory parameter by cohort and dose level.

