11.5.4. Physical Examination

A summary table of Physical Examination parameters by Body System and Visit will be provided in the TLFs.

11.5.5. 12-ECG

A summary table of 12-Lead ECG interpretation by Visit will be provided in the TLFs. Similarly, changes from baseline for each post baseline visit will be summarised.

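### ECG is part of the Part 2 primary endpoint, but the SAP summarises it only by visit, names no QT correction formula, and plans no count of patients by worst QTc or largest rise

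*Protocol*

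**What the plan says.** Protocol Table 2 makes ECG part of the Part 2 primary endpoint: "The number and frequency of AE, safety laboratory, vital signs and ECG assessments". SAP 5.4.1 repeats this. Neither attaches a variable or statistic to it, and Protocol 8.8 rules out formal statistical analysis of safety data.

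On acquisition, Protocol 5.3.8 says "All efforts should be made to ensure that an identical ECG machine is used to collect traces for individual patients" and "The Investigator or designated physician will review the ECG results". It specifies no central reading, no replicate tracings and no correction formula.

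On analysis, SAP 11.5.5 says "A summary table of 12-Lead ECG interpretation by Visit will be provided in the TLFs" (Table 2.14). SAP 11.5 gives the categories as normal, abnormal not clinically significant and abnormal clinically significant. It adds: "For ECG and hematology, clinical chemistry, coagulation and bone marrow laboratory data, the change from baseline will be summarized for each post baseline visit" (Table 2.14.1). SAP 11.2 fixes the statistics for continuous variables as n, mean, median, SD, minimum and maximum. SAP 11.5 plans shift tables to the worst post-baseline value for haematology and clinical chemistry only. The SAP nowhere mentions QTc.

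QTc values appear in the protocol only at entry. Exclusion criterion 19 sets 480 ms as the limit, and its note says "QTc values up to 500 ms will be acceptable" where a known, well-controlled condition explains the prolongation.

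SAP 7.2.2 defines baseline as the latest non-missing value up to and including the date of the first dose.

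**The concern.** QT safety is mainly a question about individuals: how many patients had a long QTc, or a large rise, at any time on treatment. Protocol 1.3 gives a reason to ask, since "SEL24/MEN1703 inhibited hERG tail current in HEK293 cells stably transfected with hERG cDNA" (IC50 values of 3.561 and 2.5 µM in two evaluations), and criterion 19 shows that the sponsor regards QTc as relevant to who may enter.

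By-visit tables do not answer that question. They describe each visit separately and cannot be added up into a number of patients. The clinically significant label and the adverse-event route do identify patients, but both depend on local judgement without a stated numeric criterion. At stake is whether the report can state a patient count for a component of its own primary endpoint.

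**Working it through.** The documents give no ECG figure to reproduce and no formal sample size. The check is a comparison of planned outputs, followed by illustrations whose ECG inputs are assumptions. Cohort sizes come from the Protocol synopsis: 23 all-comers and about 20 IDH mutants.

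**1. What each planned output can show**
- Table 2.14: readings in each category at each visit; not patients ever abnormal, and no milliseconds.
- Table 2.14.1: distribution of change at each visit, parameter unnamed. If QTc is included, the maximum shows the largest rise at that visit. It does not show how many patients passed a given value, or whether maxima at two visits belong to one patient.
- Listing 4.17: individual data, not summarised.
- Adverse-event tables: patients whose abnormality the investigator judged clinically significant, by grade.
- Patients by worst post-baseline QTc or largest rise: not planned.

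**2. Effect of one outlier on a visit summary**
- Shift in mean = rise / n. For +60 ms: 60/20 = 3.0 ms and 60/23 = 2.6 ms. Two such patients: 120/20 = 6.0 ms and 120/23 = 5.2 ms.
- Nineteen patients at 0 and one at +70 ms: mean 3.5, median 0, SD 15.7, maximum 70 ms. The maximum reveals the case; the mean and median do not.

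**3. What a patient count would give**
- One patient: 1/20 = 5.0% (exact 95% CI 0.1% to 24.9%); 1/23 = 4.3% (0.1% to 21.9%).
- No patients: upper limit 1 − 0.025^(1/n) = 16.8% at n = 20 and 14.8% at n = 23.
- Chance of at least one case if the true rate is 5%: 1 − 0.95^n = 0.64 and 0.69.

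**4. Correction formula** (Bazett QT/RR^(1/2); Fridericia QT/RR^(1/3); RR = 60/heart rate)
- QT 400 ms at 90 bpm: 489.9 against 457.9 ms, a gap of 32 ms that straddles 480 ms.
- The gap does not fully cancel in within-patient change when heart rate moves. From QT 400 ms at 80 bpm to QT 380 ms at 100 bpm, Bazett gives 490.6 − 461.9 = +28.7 ms and Fridericia gives 450.5 − 440.3 = +10.3 ms. The same two tracings differ in change by 18.4 ms.

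**5. Baseline and timing**
- Footnote 6 to the assessment schedule puts two ECGs on Cycle 1 Day 1: pre-dose and 4-6 h post-dose. Under SAP 7.2.2 the later one falls on the date of first dose and so can be taken as baseline.
- If it is, computed change = (later − pre-dose) − (4-6 h − pre-dose). With an assumed +30 ms at 4-6 h and +60 ms later, the table shows 60 − 30 = +30 ms.
- Section 5.1 schedules the other on-treatment ECGs on Cycle 1 Day 7 and on Day 1 of later cycles, pre-dose by default. Dosing covers Days 1-14 of 21, so the later-cycle tracings normally follow a week without drug. The 4-6 h tracing is the only scheduled ECG with a stated post-dose time, and the rule could remove it from the post-baseline data.

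**The case against.** The case against is substantial. Minimum and maximum are planned, so a large rise would be printed. Listing 4.17 and Protocol 8.8 provide individual data, and cohorts of about 20 can be read by eye. Clinically significant ECG abnormalities are adverse events (Protocol 7.2), graded by CTCAE v4.03 and tabulated by preferred term, with separate tables for Grade 3 and above. Dogs given 5, 10 and 20 mg/kg showed no change in ECG intervals under telemetry (Protocol 1.3), and Protocol 1.5 does not list QT prolongation among the identified clinical risks. Local reading is not a defect in an open-label descriptive study.

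All of this stands, and it limits the point. A reader might infer three stronger things that the documents do not support:
- That outliers are averaged away because only mean change is shown. SAP 11.2 plans more than the mean, and the listing and adverse-event routes exist.
- That Table 2.14.1 pools machine-printed QTc under mixed formulas. The protocol asks for the same machine within a patient and is silent on how QTc is obtained; the SAP does not say QTc is the variable. The supportable statement is that no formula is specified.
- That patients may cross the protocol's on-study QTc limits unnoticed. The 480 and 500 ms values are entry conditions; no on-study limit is stated.

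The objection does not supply the missing summary. Visit maxima do not give a number of patients, a listing leaves the counting to the reader, and the other routes rest on local judgement. The SAP already accepts the worst-post-baseline principle for two laboratory panels in the same primary endpoint.

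**Conclusion.** The point holds as a gap in summarisation and definition, not as a loss of information. For a named component of the Part 2 primary endpoint, the SAP specifies no parameter, no correction formula and no patient-level worst-value summary, and its baseline rule permits a post-dose tracing as baseline.

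The consequence is moderate: the report could show extreme values but would have no planned table, based on the measurements, stating how many patients had marked QTc prolongation. The illustrations (a 2.6 to 3.0 ms mean shift from one +60 ms rise; a 32 ms formula gap at 90 bpm) rest on assumed QT, heart-rate and rise values; they show possible size, not what occurred. The hERG finding gives a reason to look and the clean dog telemetry lowers the expectation of finding anything, so this is a worthwhile inexpensive improvement rather than a threat to the study's conclusions.

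**What to change.** In SAP 11.5 and 11.5.5, before database lock:
- Name the ECG parameters to be summarised, including QTc.
- State one QT correction formula (for example Fridericia), computed from recorded QT and heart rate where these are held; otherwise use the recorded QTc and say so.
- Define ECG baseline as the last tracing before the first dose, and apply it in Table 2.14.1 too, so that two baselines do not coexist.
- Add one table by cohort and dose, over all scheduled and unscheduled post-dose ECGs: number and percentage of patients by worst QTc category and by maximum increase from baseline. Use 480 and 500 ms from criterion 19 purely as reporting cut-points, not on-treatment rules. Cut-points for the increase, such as 30 and 60 ms, do not appear in the documents and are for the sponsor to confirm.

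Keep Tables 2.14 and 2.14.1 and Listing 4.17. The cost is SAP wording, a little programming and one table from ECGs already collected, with no added patient burden. The limitation is that a common formula can be applied only if QT and heart rate are in the eCRF; if not, recorded QTc can still be counted, with the formula uncertainty stated.

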### 5.3.9. Echocardiogram

An echocardiography assessment will be performed at Screening with follow up assessments as clinically indicated. This cardiac assessment may be performed by a MUGA scan if this is the standard, local method used.

### 5.3.10. Bone marrow assessment

A bone marrow aspirate (or biopsy where obtaining an aspirate is not possible), will be taken at the times specified in the Schedule of Study Assessment (Table 5). A local bone marrow differential assessment, to determine the % of different bone marrow cellular subpopulations, including the % leukemic blasts, will be conducted at Screening. In addition to the optional time points reported in the Schedule of Study Assessment, bone marrow assessment is mandatory at Screening and as soon as the peripheral lab results become consistent with an objective response. Bone marrow aspirates/biopsy will be tested for the genetic profile of AML cells (see [Section 5.3.13](#)). An aliquot of bone marrow aspirate/biopsy will be centrally stored for future analysis (e.g. minimal residual disease), if any.

Results from these assessments will contribute to each patient's disease assessment (see [Section 5.3.11](#)).

### 5.3.11. Disease evaluation

Evaluation of disease status will be performed at the time-points described in the Schedule of Study Assessment (Table 5), according to the AML Response Criteria in [Appendix D](#).

Disease assessment will involve evaluation of leukemic blast proportion in the bone marrow. Hematologic parameters from the routine local assessments including blast percentage (where applicable), platelet count, and other relevant parameters such as transfusion dependence will also contribute to this assessment.

To note, disease assessment must be performed as soon as the peripheral lab results become consistent with an objective response. Disease assessment will also include an aliquot of bone marrow aspirate/biopsy that will be centrally stored for future analysis (e.g. minimal residual disease), if any. In case bone marrow aspirate/biopsy is consistent with CRi or better response but still a minimal percentage of peripheral blasts is detected, the response assessment can be postponed up to 2 weeks and will be based on repeated peripheral blood results and last bone marrow aspiration results.

